8.1.2 Secondary study parameters/endpoints (if applicable)

User's experiences:

- Usability (layout, interface, ease of use, relevance of content, etc.)
- Perceived barriers and facilitators for using the sticky reminders and the app within one's daily routine. It is not being used as part of clinical care
- Perceived positive and negative effects of the sticky reminders and the app

Healthcare Professionals' Perspective

- Usefulness of information from the sticky reminder app.
- Perceived barriers and facilitators for using the information from the sticky reminders plus app within one's daily workload. How does this affect their workload?

Feasibility

- Users' experiences
- Effect on self-efficacy
- Potential as an empowering tool for physiotherapy exercises

8.1.3 Other study parameters (if applicable)

[figure not shown]
- Frequency of App use. To prove that observed effects could be a result of the intervention, we will determine app usage. We will calculate how often (times per day) the App is used during the research period
- Demography. In the questionnaires, we will ask for age, gender, marital status, medical history (regarding physiotherapy), estimated years affected by symptoms or disorder, employment and highest educational level.

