2. OBJECTIVES

Primary Objective:

To study whether NFC-equipped sticky reminders increase physiotherapy self-efficacy in home exercise programmes as compared to usual care in rehabilitating patients suffering from Neuralgic Amyotrophy or a lower extremity amputation over a period of 4 weeks.

Secondary Objective(s):

To assess the usability of the app and user experiences with NFC-equipped sticky reminders for home exercise programmes in physiotherapy as perceived by rehabilitating patients suffering from Neuralgic Amyotrophy or a lower extremity amputation and how this could be improved.

Other Objective(s)

To determine whether the intervention is used, and thus whether observed effects in intervention group could be caused by the intervention.

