8. METHODS

8.1 Study parameters/endpoints

8.1.1 Main study parameter/endpoint

We will assess the self-efficacy during exercising. Self-efficacy reflects an individual's belief in his or her ability to engage in specific behaviours that will yield a desired outcome. Self-efficacy beliefs are important because the belief that one can exercise, even given constraints and impediments such as feeling tired or being busy, is associated with a greater likelihood of doing it (Neupert *et al.*, 2009).

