- Scanning the stickers is registered in the application. Using the registrations gathered by the app, the extent to which and how the app is used can be derived and correlated to possible effects on self-efficacy. This way, we can determine whether and how much the app is used, and thus whether we can link observed group effects to intervention use.
- Using the aforementioned gathered data and subsequent analyses, we will assess the feasibility.
- Demography data will be gathered by questions regarding this topic.

Measurements

Exercise Self Efficacy Scale (ESES)

Self-efficacy will be determined with the Dutch translation of the Exercise Self-Efficacy Scale, developed and validated in spinal cord injury by Nooijen *et al.* The ESES consists of 10 items about level of self-confidence with regard to performing regular physical activities and exercise (17). A sample item is: "I am confident that I can overcome barriers and challenges with regard to physical activity and exercise if I try hard enough". Respondents answer using a 4-point scale: not at all true, rarely true, sometimes true, and always true. The minimum score is 10 and the maximum score 40. A higher score indicates higher exercise self-efficacy (Nooijen *et al.*, 2013).

System Usability Scale (SUS)

[figure not shown]
We will assess usability with a Dutch translation of the validated System Usability Scale (SUS) questionnaire. The SUS gives a global view of subjective assessments of usability (Brooke, 1996). This simple questionnaire consists of 10 items with five response options; from 'strongly agree' to 'strongly disagree'. The scores range from 0 to 100, with a score of 68 considered average.

Demographics

A few generic demographic parameters will be asked in the start questionnaire for both the intervention and control group. These include age, gender, medical history (regarding physiotherapy) and highest educational level.

Semi-structured interviews

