10.1 Primary study parameter(s)

Depending on whether values are normally distributed, different tests will be executed for self-efficacy values obtained through the ESES questionnaire.

Normally distributed: Self-efficacy values between groups will be compared with paired samples t-test (within and between control or intervention group). These tests will be performed between “before” and “after” self-efficacy values of both control and intervention group.

Not normally distributed: Self-efficacy values between groups will be compared with either a Wilcoxon signed rank test (within and between control or intervention group).

These tests will be performed between “before” and “after” self-efficacy values of both control and intervention group.

As exploratory analyses, self-efficacy values will be correlated with system usability, frequency of use (e.g. using the Pearson or Spearman’s rho test, depending on normality of the values) or tested for differences within demographic parameters (independent samples t-tests and/or linear regression).

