10.3 Other study parameters

Frequency of use

Correlation between frequency of use data from the app registrations and self-efficacy will be tested (e.g. with a Pearson or Spearman's rho test, depending on normality of the values).

Demography

Differences between the self-efficacy of groups within demographic categories (age, gender, marital status, employment status, highest educational level, estimated years affected by symptoms or disorder and medical history regarding physiotherapy) will be tested for significance using independent samples t-tests and/or linear regression.

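### The exploratory correlation of app use with self-efficacy uses a raw count without baseline adjustment, so it cannot link group effects to app use as section 8.3 intends

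*Protocol*

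**What the plan says.** The other objective in section 2 is "To determine whether the intervention is used, and thus whether observed effects in intervention group could be caused by the intervention". Section 8.1.3 repeats the aim, "To prove that observed effects could be a result of the intervention, we will determine app usage", and sets the measure: "We will calculate how often (times per day) the App is used during the research period".

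Under the parameter assessments in section 8.3, scan registrations are the source from which "the extent to which and how the app is used can be derived and correlated to possible effects on self-efficacy". The next sentence draws the inference from this: the investigators will know whether and how far the app is used, "thus whether we can link observed group effects to intervention use".

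The test is in section 10.3: "Correlation between frequency of use data from the app registrations and self-efficacy will be tested", by Pearson or Spearman according to normality. Section 10.1 gives its status: "As exploratory analyses, self-efficacy values will be correlated with system usability, frequency of use".

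None of these sections says whether self-efficacy here means the baseline score, the week-4 score or the change. None names a covariate, or a denominator for the count.

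Three other statements bear on the point. Section 8.1.1 says that the belief that one can exercise "is associated with a greater likelihood of doing it", and section 8.3 lists predictor of health behaviour among the roles of self-efficacy. Section 3 (home registration) ties each patient's exercises to one or more tags. Section 6.1 says that the app shows patients how many exercises they have been given and how many remain.

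**The concern.** The step in section 8.3 from a correlation to a link between group effects and use needs the correlation to be near zero when the app has no effect. The protocol's own theory says that it need not be. If self-efficacy drives exercising, and exercising produces scans, then patients who start with higher ESES will scan more. ESES at week 4 will also resemble ESES at baseline. Use and week-4 ESES are then correlated through baseline alone.

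The count has a second weakness. Times per day rises with the number of exercises given as well as with adherence, so two equally adherent patients with different programmes get different values.

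At stake is how the pilot is read. A positive correlation could be presented as support for the app when it only reflects who was confident at the start. A real link could also be missed in so small a group.

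**Working it through.** The protocol states no expected correlation, ESES standard deviation or power, so there is no figure to reproduce. Section 4.4 gives 30 patients in total and no split. I assume 15 in the intervention group (range 10 to 20) and a two-sided test at 0.05 (section 10 gives 0.05 but not the sidedness). All correlations below are assumptions.

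**1. Spurious correlation with the week-4 score.** Let *a* be the correlation of use with baseline ESES and *ρ* the correlation of baseline with week-4 ESES. If the app has no effect, use and week-4 ESES are related only through baseline, so r = a × ρ.
- Low end: 0.3 × 0.6 = 0.18
- High end: 0.5 × 0.8 = 0.40

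**2. The same with the change score.** With equal variances at both visits, r = −a × √((1 − ρ)/2).
- Smallest: −0.3 × √(0.2/2) = −0.09
- Largest: −0.5 × √(0.4/2) = −0.22

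The sign turns negative because patients who start high gain less on average. Choosing change over end score reverses the bias and does not remove it.

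**3. Simulation with no app effect** (n = 15, 20,000 replicates). Each cell gives the mean r and the percentage with p<0.05; the nominal rate is 5%.

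| a | ρ | Week-4 ESES, unadjusted | Change | Week-4 ESES, adjusted for baseline |
|---|---|---|---|---|
| 0.3 | 0.5 | 0.14; 8.4% | −0.15; 8.3% | 0.00; 5.4% |
| 0.3 | 0.7 | 0.20; 11.3% | −0.11; 6.9% | 0.00; 5.0% |
| 0.3 | 0.8 | 0.23; 13.8% | −0.10; 6.3% | 0.00; 5.1% |
| 0.5 | 0.5 | 0.24; 14.6% | −0.24; 14.6% | 0.00; 5.3% |
| 0.5 | 0.7 | 0.34; 24.8% | −0.18; 10.4% | 0.00; 5.0% |
| 0.5 | 0.8 | 0.39; 32.4% | −0.15; 8.6% | 0.00; 5.0% |

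**4. Number of exercises given.** Use was simulated as adherence times prescribed count, in two diagnosis groups of 8 and 7 patients. One group had 1.5 to 3 times as many exercises, and the app had no effect.
- ESES equal in the two groups: mean r about 0, p<0.05 in about 5%.
- ESES 0.5 SD higher in the group with more exercises: mean r 0.15 to 0.22, p<0.05 in 8 to 12%.
- ESES 1 SD higher: mean r 0.29 to 0.40, p<0.05 in 17 to 33%.
- Use divided by prescribed count: mean r about 0 and about 5% in every setting.

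The count therefore biases the result only if it is related to ESES. Otherwise it adds noise.

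**5. Precision.** The smallest significant |r| is t/√(n − 2 + t²). At n = 15, t = 2.160, so 2.160/√(13 + 4.667) = 0.51. It is 0.63 at n = 10 and 0.44 at n = 20. For 80% power the true r must be about tanh((1.960 + 0.842)/√12) = 0.67 at n = 15 (0.79 at n = 10, 0.59 at n = 20).

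For an observed r of 0.35 at n = 15, the Fisher interval is tanh(0.365 ± 1.960/√12), which is −0.20 to 0.73. For a partial correlation with one covariate, √12 becomes √11 and the interval is −0.22 to 0.74, so adjustment costs little precision.

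**The case against.** The case for leaving the text alone is substantial, and most of it limits the point.

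- A reader might infer that the protocol means the correlation to prove the app's effect. It does not say so. In section 8.1.3 the word attaches to determining usage, and to effects that could be a result of the intervention. Section 2 reads the same way. Checking that the app was used is a legitimate necessary condition.
- A reader might infer that this correlation is the only analysis for the other objective. It is not. The logged counts in sections 8.1.3 and 8.3 answer directly whether the app was used.
- A reader might infer that use is to be correlated with the raw score and not with change. That is not fixed. Sections 10.1 and 10.3 leave it open, and section 8.3 speaks of possible effects, which points towards change. The exact outcome could be settled in an analysis plan.
- A reader might infer that prescription size is an established confounder. The documents give no exercise counts by diagnosis and no relation between counts and ESES. Section 6.1 shows only that session frequency and type of video differ between the diagnoses.
- Section 10.1 calls the correlation exploratory, and section 4.4 says openly that no power analysis was done. A spurious r of 0.18 to 0.40 lies below the 0.51 needed at n = 15, so most such trials would show nothing significant.

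These points lower the severity. They do not remove the defect. The protocol itself fixes the raw count, the type of test and the inference in section 8.3, and that inference fails on either reading of the outcome.

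**Conclusion.** The concern holds as a minor point. An unadjusted correlation of a raw count with self-efficacy cannot show whether group effects are linked to use, because prior self-efficacy is a plausible common cause on the protocol's own account. Under assumed correlations of 0.3 to 0.5 (use with baseline) and 0.6 to 0.8 (baseline with week 4), the bias in r is +0.18 to +0.40 for the week-4 score and −0.09 to −0.22 for change. If use were unrelated to baseline ESES, this bias would be nil. Mixing adherence with number of exercises certainly makes the count harder to interpret. Whether it also biases r depends on a relation with ESES that the documents do not state.

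**What to change.** 1. In sections 10.1 and 10.3, relate use to week-4 ESES adjusted for baseline ESES, by partial correlation or regression. Both groups already complete ESES at baseline.
2. In section 8.1.3, express use as exercise-tag scans divided by prescribed exercises for each patient over the four weeks. The end-of-day report scan described in section 3 should not count in the numerator.
3. Report the estimate with its confidence interval and make no significance claim.
4. In sections 8.1.3 and 8.3, limit the stated purpose to describing whether, and to what extent, the intervention was used. Leave any attribution to the comparison between groups, which has its own limits because section 4.2 concedes that allocation is not fully random.

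The cost is some wording, one covariate in a small sample, and one denominator based on a number the app already displays. The adjustment does not make the analysis causal: other drivers of use, such as general motivation, stay uncontrolled. In the simulations each remedy was checked only against the problem it addresses.

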8.2 Randomisation, blinding and treatment allocation

We will randomise the allocation of patients to study groups as much as possible within the patient (and NFC) availability pool. Blinding is not appropriate for this pilot.

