2. **Technology introduction:** In the first hospital visit, the patient will get all the necessary or desired information on the new technology. Following this meeting, patients have time to decide whether they want to participate in the pilot. After inclusion, patients receive help for installing the app and will get an introduction on how to use the application.
3. **Home registration:** After the regular physiotherapy appointment in the hospital, patients will receive exercises to execute in the home situation. These exercises are also linked to at least one NFC tag. These NFC tags are illustrated with a location, suitable for the exercises. Patients will discuss their personal appropriate locations for the NFC tags with their physiotherapist. When walking by the NFC tag, the patient can scan the tag with their personal smartphone, showing them a video of the corresponding exercise. All information that was previously provided in the folder is now handed to the patient via the video. The application registers the scanning of the tag on a secure server. If no prescribed exercises are performed within a predefined timeslot, the app will send a one-time push notification to the patient. At the end of the day, a tag will be scanned to show the daily report form. This daily report contains questions matching the regular treatment supplemented with questions on efficacy.
4. **Physiotherapy session:** Back in the hospital setting, the regular treatment is continued and the progress of the rehabilitation will be discussed. The app can support this session by presenting graphic representations of the daily feedback gathered with the daily reports. Step 3 and 4 will be repeated until the NFC tag trial period is over.
5. **Evaluation:** In the end, the questionnaire answered at the start is repeated as an end-measure, supplemented with a system usability scale (SUS) questionnaire. Elaborate opinions will be gathered by interviewing patients and physiotherapists in a semi-structured way. In semi-structured interviewing, a guide is used, with questions and topics that must be covered.

Sticking to your Exercises

[figure not shown]
However, in contrast to structured interviews, this conversational style of interviewing allows for gathering elaborate opinions.

The timeline is shown below. The control group and intervention group will undergo a different timeline:

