4. STUDY POPULATION

4.1 Population (base)

This study will include patients that, within their rehabilitation program, receive frequent physical therapy exercises to perform at home. These patients will be recruited from their rehabilitation by physiotherapists from within the Radboudumc. We will recruit patients with distinct situations, namely Neuralgic Amyotrophy and a lower extremity amputation who use a socket prosthesis or an osseointegrated prosthesis.

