4.2 Inclusion criteria

In order to be eligible to participate in this study, a subject must meet all of the following criteria:

Intervention group:

- Willing to participate and to provide informed consent
- Minimal remaining rehabilitation period of 4 weeks
- Access to NFC-compatible smartphone
- Within their rehabilitation program, included patients have exercises to perform at home.
- Patient is able to speak, read and understand Dutch

Control group:

- Willing to participate and to provide informed consent
- Minimal remaining rehabilitation period of 4 weeks
- Within their rehabilitation program, included patients have exercises to perform at home.
- Patient is able to speak, read and understand Dutch

These inclusion criteria show that patients who are excluded from the intervention group can be included in the control group. Therefore, patients will be asked whether they have a NFC-compatible smartphone at the start of inclusion. At this point, most Android smartphones are NFC-compatible. This makes the study not truly randomized, but seems reasonable as this is a pilot study.

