11.2 Recruitment and consent

First, eligible patients will be invited by their physiotherapists to participate in the pilot study. They will receive an information letter that explains the study in general. After a suitable period of time (1-2 weeks), follow-up telephone contact will explore whether subjects are interested, the purpose of the study and study procedures will be explained and interested patients will receive an extensive information package. The initial information letter and the informed consent form are attached as separate documents.

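### Section 8.2 makes randomisation conditional even for patients with an NFC phone, who qualify for both groups, and nothing in the protocol conceals the assignment or places it after consent

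*Protocol*

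**What the plan says.** Protocol section 8.2 gives the allocation rule in one sentence, "We will randomise the allocation of patients to study groups as much as possible within the patient (and NFC) availability pool", followed by "Blinding is not appropriate for this pilot". It states no ratio, no way of generating the sequence, no concealment, no allocator, and no limit on when a patient may be placed without randomisation.

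Section 4.2 sets separate criteria for the two groups. They differ in one item, access to an NFC-compatible phone, which only the intervention group needs. The section draws the consequence itself: "These inclusion criteria show that patients who are excluded from the intervention group can be included in the control group". It then concedes: "This makes the study not truly randomized, but seems reasonable as this is a pilot study".

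On recruitment, section 4.1 says "These patients will be recruited from their rehabilitation by physiotherapists from within the Radboudumc" and section 11.2 says "First, eligible patients will be invited by their physiotherapists to participate in the pilot study". Section 3 describes the introduction to the technology at the first hospital visit and continues: "Following this meeting, patients have time to decide whether they want to participate in the pilot".

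The primary objective in section 2 is comparative: "To study whether NFC-equipped sticky reminders increase physiotherapy self-efficacy in home exercise programmes as compared to usual care". The endpoint is the ESES, a self-reported score from 10 to 40 (section 8.3).

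**The concern.** The concession in 4.2 rests on a practical fact: a patient without the right phone cannot receive the app. Nothing comparable applies to a patient who has one. For these patients randomisation is possible, and it is the only feature that would protect the comparison with usual care. Section 8.2 nevertheless qualifies it, and names patient availability next to NFC availability as a limit without saying what that means.

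Three features make the gap matter. Group membership is open. The people who bring patients into the study also treat them. And the outcome is a patient's own rating of confidence in exercising, which plausibly relates to how well suited to an app that patient appears. If an assignment can be foreseen or adjusted, the two groups of phone owners may differ before treatment in ways that bear on the ESES. The protocol gives the control group the task of separating the effect of the intervention from that of ordinary treatment (section 3), and section 4.4 expects the data to help size later randomised trials. Both uses depend on the comparison being fair.

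**Working it through.** The protocol has no figure to reproduce: section 4.4 states that no formal power analysis was done. The check is mainly textual.

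**Who can be randomised (4.2 against 8.2)**
- Patients without an NFC phone are eligible for control only. They cannot be randomised, and 4.2 says so.
- Patients with an NFC phone meet every criterion of both groups. They can all be randomised, and 4.2 gives no reason not to.
- Section 8.2 applies one conditional rule to both kinds of patient. Its condition is wider than the reason in 4.2.

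**When the assignment is known (3 against 8.3)**
- Section 3 says that controls carry out only steps 1 and 5. Step 2, the technology introduction, therefore belongs to the intervention group, yet within it the patient is still deciding whether to take part.
- Section 8.3 has both groups complete the start questionnaire after inclusion, then follow regular treatment or receive the product.
- Neither section says that allocation follows consent and the baseline ESES. Read literally, section 3 lets the intended group be known before the decision.

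**Illustration of size**

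Inputs from the protocol: 30 patients in total (4.4) and a significance threshold of 0.05 (10). Assumptions: 15 per group, a two-sided two-sample t-test, no true effect, a number *k* of patients placed by choice with the half judged more promising given the app, and a correlation *r* between that judgement and ESES change.

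The mean of the upper half of a normal distribution lies √(2/π) = 0.798 SD above its centre, so the two halves differ by 1.596 SD. In large samples:

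bias ≈ (*k*/30) × *r* × 1.596 SD

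- *k* = 10, *r* = 0.3: 0.333 × 0.3 × 1.596 = 0.16 SD
- *k* = 14, *r* = 0.3: 0.467 × 0.3 × 1.596 = 0.22 SD

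With so few patients the halves lie slightly closer together. Simulation with 8,000 runs per setting gives:

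| Placed by choice | *r* | Bias (SD) | False-positive rate |
|---|---|---|---|
| 0 of 30 | any | 0.00 | 5% |
| 10 of 30 | 0.2 | 0.10 | 5% |
| 10 of 30 | 0.3 | 0.14 | 6% |
| 10 of 30 | 0.5 | 0.26 | 10% |
| 14 of 30 | 0.2 | 0.14 | 6% |
| 14 of 30 | 0.3 | 0.21 | 9% |
| 14 of 30 | 0.5 | 0.35 | 15% |

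A normal approximation agrees. The standard error is √(2/15) = 0.365 SD. A bias of 0.14 SD is 0.38 standard errors, giving Φ(0.38 − 1.96) + Φ(−0.38 − 1.96) = 6.7%. A bias of 0.21 SD is 0.58 standard errors, giving 8.9%. Repeat simulations agree within about 0.02 SD and one percentage point.

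**The case against.** The strongest reply is that 8.2 promises randomisation and merely notes its practical limits. On that reading all phone owners are randomised, the qualifier refers only to phone access, and 8.2 matches 4.2. The reading is natural and may be what was meant. It does not settle the matter, because patient availability is named as a separate limit and no sentence binds the randomisation of phone owners.

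A reader might go further and infer that physiotherapists assign patients, or may put keen patients on the app and hesitant ones in control. The documents do not support this. They say that physiotherapists recruit and invite, not that they allocate. Section 12.1 has researchers of the coordinating department running the study. Choosing by keenness would also not be randomising as far as possible.

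Nor do the documents show that any bias favours the app. The illustration builds in a positive correlation. Patients picked for high confidence may start near the ESES maximum of 40 and have less room to rise, which would turn the bias the other way.

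It would also be too strong to say that analysis can do nothing. Both groups complete the ESES and demographic questions at the start (8.3), so part of any imbalance would be visible. An unrecorded expectation of how a patient will change would not.

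Larger figures can be produced: with all 30 placed by choice, the false-positive rate is 25% at *r* = 0.3 and 61% at *r* = 0.5. They contradict 8.2's own wording and require every patient to own a suitable phone, so they should not be used to size this problem.

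Finally, this is an exploratory pilot that openly says it is not truly randomised. That excuses low power and the control patients without phones. It does not cover phone owners, for whom a binding rule costs almost nothing.

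**Conclusion.** The point holds in a limited form. Section 8.2 leaves random allocation non-binding for patients who could enter either group, and 4.2 gives no reason for that. In an open study recruited by treating physiotherapists, with no concealment and no stated order of consent and assignment, selection bias among phone owners is possible. The text permits it but does not say that it will occur.

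Size and direction are unknown. The figures of about 0.14 to 0.21 SD and 6 to 9% rest on an assumed 15:15 split, 10 to 14 of 30 placed by choice, a correlation of 0.3 and a two-sample t-test. That test is an assumption too, since section 10.1 names paired tests. With fewer patients placed by choice or a weaker correlation the effect is slight.

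This is not detail that can wait for a statistical analysis plan, because the protocol itself fixes the allocation rule. It should be changed, but it does not invalidate the feasibility and user-experience aims.

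**What to change.** Replace the allocation sentence in 8.2 with a rule such as this:

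*Every patient eligible for both groups is allocated only from a computer-generated list with randomly varying block sizes. A coordinating researcher who does not treat patients prepares and holds the list. Each assignment is released singly, after informed consent and the baseline ESES are recorded, and is not changed for reasons of availability or preference. Patients without an NFC phone may join the control group and are marked as non-randomised in the dataset.*

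Section 3 should be aligned so that the product introduction follows assignment.

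The list alone is not enough. Patients without phones still enter control, so the contrast across all patients stays confounded with phone access. Section 10.1 should therefore make the between-group ESES comparison in the list-randomised patients and show the comparison that includes non-randomised controls as supportive.

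The change needs a paragraph in 8.2, a sentence in 10.1 and a short list held by staff who already coordinate the study. It adds no patients or visits. The downsides are less scheduling freedom and fewer controls in the randomised comparison. For example, if 10 of 30 patients had no phone (an assumption) and the other 20 were split 10:10, the standard error would be √(1/10 + 1/10) = 0.447 SD, against √(1/10 + 1/20) = 0.387 SD with all controls. That is a modest loss for a pilot not sized for power.
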